The retrospective analysis included patients diagnosed with missed abortion by ultrasound at our outpatient clinic from January 2018 to March 2023. Patients meeting both inclusion and exclusion criteria were consecutively enrolled. The prospective study included patients diagnosed with missed abortion by ultrasound at our outpatient clinic from December 2023 to December 2024. Patients meeting both inclusion and exclusion criteria were consecutively enrolled. General information was collected from patients in different groups, including gestational age at termination of pregnancy, symptoms, ultrasound findings of uterine size, gestational

sac size and location, serum HCG levels, parity, and whether there were other intrauterine diseases before pregnancy. Patients were grouped according to their wishes and underwent either drug or surgical treatment. Surgical time, intraoperative blood loss, type and dosage of medications, time of gestational sac expulsion, amount of vaginal bleeding, and adverse drug reactions were recorded. Follow-up included the duration and amount of vaginal bleeding after discharge, time of menstrual resumption, changes in menstrual flow, and the probability and outcome of subsequent pregnancies.

Selection criteria:

1. Retrospective analysis : Patients diagnosed with missed abortion by ultrasound at our outpatient clinic from January 2018 to March 2023 who met the inclusion criteria but did not meet the exclusion criteria were enrolled consecutively.

2. Prospective study: Patients diagnosed with missed abortion by ultrasound at our outpatient clinic from December 2023 to December 2024 who met the inclusion criteria but did not meet the exclusion criteria were enrolled consecutively.

Inclusion criteria:

① Age 18-40 years ; ② Diagnosed with early pregnancy missed abortion by imaging and laboratory examinations; ③ All indicators of routine examinations before treatment are within the normal range, and there are no serious systemic diseases; ④ No indication for emergency curettage ; ⑤ Good compliance, and follow-up observation as required (prospective study).

Exclusion criteria:

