① Those with contraindications to medical abortion; ② Those allergic to estrogen or with contraindications to estrogen use; ③ Those unable to follow up according to the follow-up plan; ④ Those with thromboembolic diseases, known or suspected breast cancer, hormone-dependent tumors, etc.; ⑤ Those with vaginal bleeding exceeding the usual menstrual flow; ⑥ Those with serious heart, liver, or kidney diseases; ⑦ Those with serious internal or surgical diseases, malignant

tumors, or mental illnesses who cannot cooperate.

Statistical methods:

using SPSS 26.0 statistical software. Quantitative data were expressed as mean \pm standard deviation, and the independent t-test was used for comparisons between groups. Count data were expressed as percentages (%), and the chi-square test was used for comparisons between groups. The rank-sum test was used for comparisons between groups of ordinal data. $P < 0.05$ was considered statistically significant.

Research Text

1. Research Background

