usual menstrual flow; ⑥ Those with serious heart, liver, or kidney diseases; ⑦ Those with serious internal or surgical diseases, malignant tumors, or mental illnesses who cannot cooperate.

4. Research Process

Grouping:

1. Retrospective analysis: Based on the different treatment methods for patients with early missed abortion, patients were divided into a drug treatment group and a surgical treatment group.

2. Prospective study: Patients with early missed abortions were grouped according to their own wishes to choose surgical or medical abortion, and to the use of different doses of estrogen before and after abortion treatment .

This study did not intervene in patient treatment; it only pre-designed and collected relevant data. No additional examinations or tests were performed on patients during the study, and all procedures were conducted according to standard clinical practice. After treatment, patients were divided into surgical and drug treatment groups based on their chosen treatment plans. Furthermore, based on the estrogen dosage chosen by the patients, they were divided into non-stimulatory estrogen, standard-dose estrogen, and high-dose estrogen groups. Data were then statistically analyzed.

Timing of treatment :

The following criteria are considered indicative of missed abortion in early pregnancy: Ultrasound diagnosis of missed abortion includes: ① Crown-rump length $\geq 7\text{mm}$, no fetal heartbeat detected. ② Average diameter of the gestational sac in the uterine cavity $\geq 25\text{mm}$, no embryo detected. ③ No yolk sac seen in the uterine cavity, and no embryo or fetal heartbeat detected after 2 weeks. ④ Yolk sac visible in the uterine cavity, and no fetal heartbeat detected after 11 days.

Treatment methods:

1. Retrospective Analysis: Patients diagnosed with early pregnancy loss at our hospital between January 2018 and March 2023 were included in this study. All patients were

informed of the available treatment options and associated risks before treatment and signed a treatment consent form. Patients were grouped according to their preferred treatment method: medication or surgery.

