For all patients with missed abortions, treatment to promote uterine contraction after the expulsion of the pregnancy tissue includes: routine intravenous administration of uterotonic agents (oxytocin is commonly used , and ergonovine may be used if

necessary) ; and oral administration of uterotonic drugs (such as Wujia Shenghua capsules) for 2 weeks. Infection prevention: If signs of infection or high-risk factors for infection are present, antibiotics may be used as appropriate, and the type, route of administration, dosage, frequency, and duration of administration of antibiotics must be accurately recorded. Pathological examination: The pregnancy tissue expelled during the procedure is routinely sent for pathological examination; chromosomal analysis of the abortion tissue is performed based on the patient's preference.

End of treatment sign:

(1) A follow-up ultrasound showed no retained products of conception, and serum HCG levels returned to normal; (2) Patients with retained products of conception underwent clinical observation or curettage.

5. Key Evaluation Indicators

(1) Evaluation indicators before treatment: patient's age, time of consultation, gestational week of termination of pregnancy, symptoms, ultrasound findings of uterine size, gestational sac size and location, serum HCG level, parity , number of previous intrauterine procedures, and whether there are other intrauterine diseases before pregnancy (such as intrauterine adhesions, uterine septum , submucosal fibroids).

(2) Routine examination data after admission: routine vaginal discharge test, HPV/TCT, routine blood tests, liver and kidney function tests, electrolyte test , coagulation function test, thyroid function test, blood β -HCG test, anti-Müllerian hormone test, pre-transfusion examination, electrocardiogram, chest X-ray, uterine and bilateral adnexa 2-D/3-D color Doppler ultrasound and other related examinations.

(3) During drug treatment: the type and dosage of drugs taken, the time of expulsion of the gestational sac, the amount of vaginal bleeding, adverse drug reactions, etc.

(4) Surgical data: Date of surgery; depth of uterus; location and size of the gestational tract; operation time (from the start of the distension procedure to the withdrawal of the endoscope); amount of intraoperative blood loss; whether there is any retained gestational tract after surgery; clarity of the intraoperative field of vision;

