volume of distension fluid in and out; whether there is a decrease in blood oxygen saturation; whether complications such as uterine perforation, acute left heart failure, or gas embolism occur. Postoperative follow-up data : serum β -HCG, complete blood count, CRP, procalcitonin (not necessary), ultrasound to check for retained gestational tract, and if so, record the maximum diameter of the retained tract.

(5) Outpatient follow-up data 3 months after treatment : duration of vaginal bleeding after miscarriage, amount of bleeding, time of menstruation resumption , changes in menstrual flow , whether ultrasound indicates intrauterine adhesions, condition of endometrium, whether intrauterine adhesion surgery was performed, and intrauterine adhesion score.

(6) Pregnancy outcomes: Pregnancy rate after 1 year of trying to conceive (followed up every 6 months) ; spontaneous abortion rate, premature birth rate, full-term birth rate, stillbirth rate in subsequent pregnancies.

Follow-up data is used only for clinical efficacy evaluation.

6. Safety considerations

The data in this study are derived from clinical data and are absolutely safe. The use of estrogen for missed abortion is in accordance with routine clinical treatment, with the standard dose being 2 mg. 4 mg of estrogen is an off-standard dose, but numerous domestic and international studies have shown that high-dose estrogen for women of childbearing age without contraindications to estrogen use can effectively improve patients' clinical symptoms and has a high safety profile.

7. Statistical Analysis

using SPSS 26.0 software. Normally distributed measurement data were expressed as ($\bar{x} \pm s$), and t-tests were used for comparisons between two groups, while ANOVA was used for comparisons among multiple groups. Non- normally distributed measurement data were expressed as the median, and a nonparametric rank-sum test was used . Categorical data were analyzed using the χ^2 test or Fisher 's test. $P < 0.05$ was considered statistically significant.

8. Data integrity and quality assurance

Researchers should ensure that data is authentic, accurate, complete, and traceable, and should ensure the integrity of basic clinical research documents during retention, avoiding intentional or unintentional alteration or loss.

9. Ethical Statement

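### The protocol names only unadjusted tests to compare groups that the women chose themselves, so differences in case mix can appear as treatment effects

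*Protocol*

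**What the plan says.** Allocation is by choice in both parts. The synopsis (Experimental procedure) states: "Patients were grouped according to their wishes and underwent either drug or surgical treatment". For the retrospective part, Research Process (Treatment methods) states: "Patients were grouped according to their preferred treatment method: medication or surgery". In the prospective part, Research Process (Grouping) adds that the estrogen dose level is also the patient's choice. This gives 12 groups, A to L.

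The comparison methods are stated twice:

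- Section 7: "t-tests were used for comparisons between two groups, while ANOVA was used for comparisons among multiple groups" for normally distributed data, a rank-sum test otherwise, and "Categorical data were analyzed using the χ^2 test or Fisher 's test".
- Synopsis, Statistical methods: "the independent t-test was used for comparisons between groups" for quantitative data, "the chi-square test was used for comparisons between groups" for counts, and a rank-sum test for ordinal data.

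In both places a P value below 0.05 "was considered statistically significant". Section 5(1) records age, gestational week, sac size and location, HCG, parity, "number of previous intrauterine procedures, and whether there are other intrauterine diseases before pregnancy". The synopsis (Experimental Design) says that the study looks for the optimal clinical treatment. Section 3 gives 400 retrospective and 180 prospective cases.

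**The concern.** Unadjusted tests suit groups that are comparable by design. These groups are not. In the prospective part a woman chooses after her condition and the risks of each option have been explained, so prognosis can influence the choice. Section 1 itself links sac size to surgical risk, and says that surgical complications may affect later pregnancies. Previous procedures and existing adhesions plausibly bear on adhesions, menstruation and later pregnancy, which are outcomes in Section 5(5) and 5(6).

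If such factors differ between groups, the stated P value tests treatment and case mix together. A larger sample does not help: the bias stays the same while the false rejection rate rises. At stake is every between-group efficacy conclusion in both parts.

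**Working it through.** **What the text fixes.** All the tests named in the two places are unadjusted. Neither place, nor any other section, mentions regression, matching, stratification, weighting or propensity scores. The protocol gives no figure for imbalance or for the strength of any risk factor, so there is no figure of its own to reproduce. The calculation below is an illustration.

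**Inputs.** The 400 cases come from Section 3. Everything else is assumed: a 200 v 200 split, a two-sided 5% test, no treatment effect, and one binary risk factor.

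**Formulas.**
- Bias = (difference in prevalence) × (difference in success).
- SE = √[p₁(1−p₁)/200 + p₂(1−p₂)/200], and z = bias/SE.
- Rejection probability = Φ(z−1.96) + Φ(−z−1.96).

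**Results.**

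| Success without → with factor | Prevalence | Success in groups | Bias | SE | z | Rejection |
|---|---|---|---|---|---|---|
| 90% → 65% | 60% v 40% | 75% v 80% | 0.20 × 0.25 = 5 points | 0.0417 | 1.20 | 22.4% |
| 90% → 65% | 65% v 35% | 73.75% v 81.25% | 0.30 × 0.25 = 7.5 points | 0.0416 | 1.80 | 43.8% |
| 90% → 75% | 60% v 40% | 81% v 84% | 0.20 × 0.15 = 3 points | 0.0380 | 0.79 | 12.4% |

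An uneven split of the 400 would change the rejection rates but not the bias.

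**Check by simulation** (20,000 runs, success 90% without and 70% with the factor, no treatment effect). The stratified test is Mantel-Haenszel on the factor.

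| Prevalence | Per group | Unadjusted rejection | Stratified rejection |
|---|---|---|---|
| 40% v 40% | 200 | 5.2% | 5.0% |
| 30% v 50% | 90 | 10.4% | 5.0% |
| 30% v 50% | 200 | 18.0% | 5.2% |
| 20% v 60% | 90 | 28.6% | 5.0% |
| 20% v 60% | 200 | 55.8% | 4.9% |

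With no imbalance the unadjusted test is sound. With imbalance, adjusting for the factor restores the nominal level. The 90 per group stands for Part II pooled into drug v surgery and split evenly (180/2).

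**How much adjustment the data can carry.**
- *Part I.* If the Section 1 background rates (81% drug, 96% surgery) held at 200 v 200, failures would number 200 × 0.19 + 200 × 0.04 = 38 + 8 = 46. A model with treatment, seven covariates and five indicators for six calendar years has 13 parameters, or 46/13 ≈ 3.5 failures each. With calendar time as one term there are 9 parameters, or 46/9 ≈ 5.1. A propensity model has 8 terms and depends on group size instead: 200/8 = 25 women per term in each group.
- *Part II.* 180/12 = 15 women per group if equal, too few for adjusted comparison across all 12. Pooling to three dose levels within each treatment type gives 180/6 = 30.

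**The case against.** The strongest objection is scope. Adjustment is often left to the SAP, and Section 7 is a short list of tests by data type that does not call itself exhaustive. But the protocol is not silent: it states twice how groups are compared, and both times with tests unsuited to self-selected groups. A SAP that adjusted would leave these passages needing correction.

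Four further points stand in part:

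- Shared eligibility removes some confounding. Contraindications, bleeding above menstrual flow, indications for emergency curettage, abnormal routine tests and serious disease are excluded in every group. Sac size, HCG, previous procedures and existing intrauterine disease remain free to differ.
- The magnitudes rest on assumed inputs. A reader might infer that the study is biased by 3 to 7.5 points, or that a drug-versus-surgery difference would be an artefact. The protocol supports neither. It gives no imbalance and no direction, and its background rates differ by 96 − 81 = 15 points, more than any bias in the three Part I illustrations.
- A reader might infer that one long covariate list can serve both parts. The counts above rule this out for 12 groups averaging 15 women.
- A reader might infer that baseline adjustment would make the estrogen results causal. It would not. In the prospective drug groups (Research Process, Treatment methods), the dose after abortion is chosen once expulsion is complete and bleeding is light. Women with partial expulsion are given estradiol valerate 2 mg twice daily, and those with none may be. Estrogen received thus partly follows the early result, which no Section 5(1) variable captures.

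**Conclusion.** The concern holds as a mismatch between a stated method and the design. Section 7 (t-test, ANOVA, rank-sum, chi-square or Fisher) and the synopsis (t-test, chi-square, rank-sum; no ANOVA) give only unadjusted tests for groups formed by choice, while the recorded confounders have no part in the comparison. Case mix can appear as a treatment effect.

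That conclusion rests on the text alone. Its size does not: 3 to 7.5 points and 12% to 44% false rejection are illustrations that depend on the assumed factor, imbalance and 200 v 200 split. The true size and direction are unknown. Adjustment reduces the problem for measured factors only.

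**What to change.** Change Section 7 and the synopsis as follows.

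- **Part I.** Make the main drug-versus-surgery comparison an adjusted one, by regression or propensity-score overlap weighting. Pre-specify a short list from Section 5(1): age, gestational week, sac size, log HCG, parity, previous intrauterine procedures and pre-existing intrauterine disease, with calendar time as a single term. Where failures are few, prefer the propensity-score approach.
- **Part II.** Limit adjusted comparisons to a few pre-specified pooled contrasts: drug v surgery, and estrogen dose level within treatment type. Use fewer covariates or a propensity score. Treat the 12-group comparison as descriptive.
- **Estrogen in the drug groups.** Restrict contrasts of the dose taken after abortion to women with complete expulsion who chose their dose, and state why. Such contrasts cannot show whether estrogen affects expulsion itself.
- **Reporting.** Keep the unadjusted tests to describe the groups. Word conclusions as adjusted associations, and state that unmeasured confounding remains.

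The covariates are already recorded, so no new data are needed. The price is wider intervals, fewer formal contrasts in Part II, and the work of defining the pooled contrasts and covariate lists before results are seen.

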labor, conduct statistical analysis on the efficacy, and evaluate whether the treatment plan achieves the desired therapeutic effect while reducing the occurrence of complications, thus providing a valid basis for the subsequent clinical treatment of missed abortion.

3. Research Design

Sample size calculation: Retrospective study of 400 cases

A prospective study of 180 cases

flow chart:

4. Research Content

This study is divided into two parts. The first part is a retrospective analysis to explore the differences in efficacy and fertility outcomes among patients with different treatment methods for missed abortion; the second part is a prospective study to explore the impact of different doses of estrogen combined with different treatment methods on the efficacy of treatment for missed abortion in early pregnancy.

Part I retrospective analysis collected data from patients with early pregnancy loss due to miscarriage who visited the Department of Gynecology at Xiangya Third Hospital of Central South University between January 2018 and March 2023. All patients had voluntarily accepted drug or surgical treatment and signed relevant treatment consent forms, and were exempted from signing informed consent forms regarding the data collection.

Part II, a prospective study, collected data from patients with early pregnancy loss due to miscarriage who visited the Department of Gynecology at Xiangya Third Hospital of Central South University between December 2023 and December 2024. All patients received either medication or surgical treatment at their own discretion. All participants were required to provide fully informed consent and sign an informed consent form.

Selection criteria:

① Age 18-40 years ; ② Diagnosed with early pregnancy missed abortion by imaging and laboratory examinations; ③ All indicators of routine examinations before treatment are within the normal range, and there are no serious systemic diseases; ④ No indication for emergency curettage ; ⑤ Good compliance, and follow-up observation as required (prospective study).

Exclusion criteria:

① Those with contraindications to medical abortion; ② Those allergic to estrogen or with contraindications to estrogen use; ③ Those unable to follow up according to the follow-up plan; ④ Those with thromboembolic diseases, known or suspected breast cancer, hormone-dependent tumors, etc.; ⑤ Those with vaginal bleeding exceeding the

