misoprostol is not expelled after medical abortion but there is no heavy vaginal bleeding, continue to administer 400µg of misoprostol sublingually or vaginally 3 hours later . The total daily dose (misoprostol) should not exceed 1800µg . If the misoprostol is still not expelled, surgical treatment may be temporarily withheld on the second day. High-dose estrogen 2mg B id can be combined to improve uterine contraction sensitivity. If the misoprostol is still not expelled, observation for one week or hysteroscopic surgery can be chosen.

③ If part of the pregnancy tissue is expelled without heavy bleeding and vaginal bleeding is less than menstrual flow, surgery may not be necessary initially. For those without contraindications, administer 2mg of estradiol valerate twice daily, check β-HCG weekly, and have a follow-up ultrasound every 2-3 weeks. If, during the waiting period, the pregnancy tissue is expelled and the remaining tissue is less than 5 mm in diameter , an artificial cycle will be initiated . After the next menstrual period, a follow-up ultrasound and HCG test will be performed, and the doctor will assess whether further surgery is needed. If heavy bleeding (more than twice the menstrual flow) occurs during the treatment, emergency hospitalization is required . If infection occurs during the treatment, emergency hospitalization is required, followed by aggressive anti-infection treatment and, depending on the circumstances, a curettage procedure may be necessary.

④ Heavy bleeding during medical abortion, with intensified uterine contractions (such as oxytocin) failing to expel the pregnancy tissue, and excessive bleeding. Examination reveals the pregnancy tissue is still within the uterine cavity, especially with no tissue impaction in the cervical canal (if present, it should be immediately removed with ovum forceps) . If bleeding significantly decreases after ovum forceps clamping , surgery is not performed immediately; instead, uterine contractions are intensified, and β-HCG is checked weekly. A follow-up ultrasound is performed in 3-4 weeks. If vaginal bleeding remains heavier than menstrual flow after clamping, emergency hysteroscopic-assisted or direct hysteroscopic surgery is necessary.

(2) Surgical treatment group: Patients clinically diagnosed with early pregnancy loss and choosing surgical treatment were grouped according to their own wishes. Group G

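### Section 7 sends continuous data to the t-test or ANOVA on normality alone, although self-chosen groups are likely to be unequal in size; Welch versions should be named for the two-group and three-dose comparisons

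*Protocol*

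**What the plan says.** Section 7 splits measurement data by distribution. The t-test and ANOVA branch opens with "Normally distributed measurement data were expressed as" and continues that "t-tests were used for comparisons between two groups, while ANOVA was used for comparisons among multiple groups". For data that are not normal, "a nonparametric rank-sum test was used". Nothing is said about equality of variances, and no unequal-variance version is named. The significance threshold is 0.05, with sidedness not stated.

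The synopsis, under Statistical methods, is looser. For all quantitative data "the independent t-test was used for comparisons between groups", without even the normality condition, and the rank-sum test is reserved there for ordinal data.

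On group sizes, Section 3 gives only totals: "Retrospective study of 400 cases" and 180 prospective cases. Section 4 (Research Process, Grouping) says of the prospective part that "Patients with early missed abortions were grouped according to their own wishes to choose surgical or medical abortion". It then forms three groups by the estrogen dose the patient chose (none, standard, high). The treatment descriptions subdivide the prospective patients further into groups A to L. No ratio, quota or planned group size is given.

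**The concern.** An unqualified t-test or ANOVA is ordinarily the version that pools the group variances. Pooling does little harm when group sizes are about equal or variances are alike. When both differ, the standard error is wrong. If the smaller group is the more variable, the test rejects too often. If the larger group is, it rejects too seldom and real differences are missed.

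This design removes the usual protection of near-equal sizes, because no allocation is controlled. Unequal spread is plausible too. The drug pathway has several courses, including repeat dosing and a point at which "observation for one week or hysteroscopic surgery can be chosen", whereas the surgical pathway is a scheduled procedure. The Section 7 fallback does not cover this, since it is triggered by non-normality and not by unequal variance.

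At stake is the calibration of P values and confidence intervals for mean differences in outcomes that stay on the normal branch.

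**Working it through.** **Inputs from the protocol.** Totals of 180 and 400 (Section 3); threshold 0.05 (Section 7), taken as two-sided; groups by patient choice (Section 4). The sample sizes cannot be reproduced, because no effect, SD, rate, power or allocation ratio is given.

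**Inputs that are assumptions.** The split between groups and the ratio of SDs; normal data; equal true means.

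**Formula, two groups.** With sizes n₁, n₂ and SDs s₁, s₂:

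- pooled variance: v = [(n₁−1)s₁² + (n₂−1)s₂²]/(n₁+n₂−2)
- squared SE used by the test: v(1/n₁ + 1/n₂)
- true squared SE: s₁²/n₁ + s₂²/n₂
- approximate error rate: 2[1 − Φ(t_crit × SE used / SE true)], with t_crit = 1.973 on 178 degrees of freedom

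**Worked case: 120 v 60, SD ratio 2.**

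- Smaller group more variable: v = (119×1 + 59×4)/178 = 1.994. SE used² = 1.994 × 0.025 = 0.0499. SE true² = 1/120 + 4/60 = 0.0750. SE ratio = √0.665 = 0.815. 1.973 × 0.815 = 1.609, so the error rate is 10.8%.
- Larger group more variable: v = (119×4 + 59×1)/178 = 3.006. SE used² = 0.0751. SE true² = 4/120 + 1/60 = 0.0500. SE ratio = √1.503 = 1.226. 1.973 × 1.226 = 2.419, so the error rate is 1.6%.

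**Range of cases** (formula / simulation of 10,000 runs; simulation standard error about 0.2 points at 5%, since √(0.05×0.95/10,000) = 0.0022):

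| Sizes | SD ratio | Pooled, larger group more variable | Pooled, smaller group more variable | Welch (simulated, same order) |
|---|---|---|---|---|
| 90 v 90 | 2 | 4.9% / 4.7% | 4.9% / 4.9% | 4.6%, 4.9% |
| 108 v 72 | 1.5 | 3.3% / 3.6% | 6.8% / 7.1% | 5.1%, 5.4% |
| 120 v 60 | 2 | 1.6% / 1.7% | 10.8% / 10.9% | 4.9%, 5.0% |
| 135 v 45 | 2 | 0.7% / 0.9% | 14.9% / 14.9% | 5.6%, 5.1% |
| 300 v 100 | 2 | 0.7% / 0.8% | 15.0% / 15.4% | 4.9%, 5.0% |

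The first row is the baseline check: equal sizes recover 5% despite a twofold SD ratio. A second simulation of the 108 v 72 case gave 3.5% and 6.6%, so about 3.5% and 7% is a fair summary. The last row shows that the larger retrospective total does not help.

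**Three dose groups** (20,000 runs): sizes 100/50/30 with SDs 1/1.5/2 give 13.3% for classical ANOVA and 5.4% for Welch's ANOVA. With the SDs reversed, the figures are 1.8% and 5.0%.

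**Twelve lettered groups.** 180/12 = 15 women per group on average. An assumed unequal layout (40, 30, 20, 20, 15, 15, 10, 10, 5, 5, 5, 5; total 180) with SDs running from 1 to 2 gives, for classical ANOVA, 21.8% when the smaller groups are more variable and 1.3% when the larger ones are. Welch's ANOVA gives 8.6% and 8.1%. With equal SDs, in two assumed size patterns with a smallest group of 5, classical ANOVA holds 5.1–5.2% while Welch's runs at 7.4–8.6%.

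**The case against.** The best reply is that the protocol nowhere says variances are pooled. The words t-test and ANOVA do not exclude the Welch forms, and variance handling is often left to a statistical analysis plan, which is not at hand. That stands as a limit: this is not a demonstrated error. It does not dispose of the point, because the protocol does fix its tests and the condition for using them, and that condition omits the one that self-chosen group sizes make relevant.

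Second, the evidence for unequal spread is indirect. If some drug patients expel tissue early and others wait weeks, the data are likely to be skewed, and Section 7 then sends them to the rank-sum test. This also stands, though only for Section 7, since the synopsis keeps all quantitative data on the t-test. Several recorded items are not drug-against-surgery means at all. Expulsion time is recorded during drug treatment, operation time and intraoperative blood loss are surgical data, and adhesions, pregnancy and birth outcomes are yes/no items or rates. So a reader should not infer that every P value for a mean is affected.

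Third, Welch's method is not free of cost everywhere. With twelve groups, some of about five women, it exceeds 5% even when SDs are equal and classical ANOVA is sound. That objection is correct and limits the fix.

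Fourth, in self-selected groups confounding governs what any P value means. That is also true; it is a separate matter which this change does not touch.

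**Conclusion.** The point holds as a minor one. Section 7 makes normality the sole condition, the synopsis makes none, and group sizes are left to choice. If sizes and variances both differ, the usual pooled tests depart from 5% for outcomes kept as normal. The departure is modest under mild assumptions (about 3.5% or 7%) and large under strong ones (about 1% or 15% at 3:1 with a twofold SD ratio; about 13% in the three-dose example).

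A reader might infer that the groups are bound to differ in spread, or that an error rate of 1% or 15% is a property of this study. The document supports neither. It reports no SD and no group size, unequal size is likely rather than certain, and with equal group sizes the two-group test stays near 5% even at a twofold SD ratio. The figures show sensitivity, not an expected error rate.

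**What to change.** In Section 7, and in matching words in the synopsis, replace the t-test and ANOVA wording with something like: *For measurement data treated as normally distributed, drug and surgery are compared by Welch's t-test and the three estrogen-dose groups by Welch's ANOVA; mean differences are given with 95% confidence intervals that do not assume equal variances.* The synopsis should also carry the same normality condition as Section 7.

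Limit the sentence to those two comparisons. If an overall test across groups A to L is kept, it needs its own decision: with groups as small as five, neither ANOVA version can be relied on for 5%, and Welch's should not be offered there as the remedy.

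The cost is one sentence in two places. Both procedures are available in the SPSS version the protocol names. With two equal groups the pooled and Welch tests have practically the same error rate, so little is lost if the concern about spread proves unfounded. Naming the version now also prevents a choice between versions after results are seen.
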